7.4 Follow-up

Study staff will contact dosimetry and rest/stress participants by phone following the administration of [⁶⁸Ga]Galmydar to confirm the subject's well-being and to ascertain if an adverse event (AE) occurred post-imaging procedures. If any of the specified days are not business days, the phone call may occur the following business day. In the event of a serious AE or unanticipated problem, we will ask participants to return to the imaging facility for evaluation/safety visit. Follow-up may

consist of an in-person visit(s) or additional telephone contact. Study staff may access medical records during the study to follow AE/problems that developed because of study participation. We will follow all participant AEs until resolution or stabilization, as evaluated by the PI or designee. Study participation is complete at the end of the follow-up or the final monitoring visit of serious AEs.

7.4.1 Dosimetry group

Dosimetry subjects will receive a phone call within 2-3 days and repeated at 5-7 days or as late as 14 days post [⁶⁸Ga]Galmydar injection.

7.4.2 Rest/Stress group

Rest/stress participants will receive a phone call within 2-3 days post [⁶⁸Ga]Galmydar injection. The follow-up phone call to collect safety data must be complete before scheduling a participant for the rest/stress ¹³N-ammonia PET imaging visit.

8 IMAGE PROCESSING AND ANALYSIS

8.1 Rest Stress Group

8.1.1 PET Images

All images will be reconstructed at 5-min (a delay to allow for blood-pool clearance) using reconstruction matrix at 168 × 168 × 109, with a pixel size (2 × 2 × 2 mm). Scatter, decay, and random corrections will also be applied to the reconstructed images. Static myocardium perfusion and gated myocardial function images will be generated by skipping the first 5 minutes of the list mode data acquisition. Dynamic image sequence will be reconstructed for quantitative blood flow evaluation. Comparative quantitative blood flow will be evaluated with Carimas and also using QPET or 4DM software⁶⁵ available through our departmental image processing servers (MIM/Vista and Hermes). Myocardial image processing techniques will then be applied to the gated datasets. The myocardial wall segment analysis will be performed using the 17-segment American Heart Association model⁶⁶.

8.1.2 MPI Interpretation

All images will be interpreted and blindly scored by a board certified radiologists (Drs. [name], [name], and [name]) in nuclear medicine. Both overall qualitative diagnosis and semi-quantitative 17 segment with 5 point (0=normal, 4=absent tracer uptake) scoring will be employed in the independent blind read out by 3 expert radiologists in PET MPI interpretation. To maintain consistency, the same three readers will interpret all PET studies in independent reading sessions. Importantly, these readers will be blinded to type of radiotracer, the presence or absence of stress agent, and all clinically relevant data. Image quality will also be classified as excellent, good, fair, poor, or uninterpretable. For purpose of assessing diagnostic efficacy, each blinded reader will rate the rest/stress perfusion and gated images as normal, ischemic, ischemic and scar, or scar. A

patient will be defined as MPI negative if the rating will be normal. Summed stress scores (SSS), summed rest scores (SRS), and summed difference scores (SDS) will also be calculated ⁶⁴. Absolute regional myocardial blood flow will also be reported.

8.1.3 Coronary Angiography Interpretation

All coronary angiograms will be interpreted using quantitative coronary analysis (QCA). Separate research analysis of the anonymized data will be performed. A coronary stenosis will be considered present when there is = 50% diameter stenosis in any epicardial coronary artery. The presence of one or more coronary stenosis will be used to define the presence of significant CAD. Presence or absence of wall motion abnormality will not be considered in interpreting the presence or absence of CAD. The determination of the presence or absence of CAD will be strictly related to coronary stenosis in the native coronary arteries; arteries with patent stents will be classified as no significant CAD, regardless of evidence of prior myocardial infarction. Arteries with bypass grafts but native coronary stenosis will be classified as significant CAD.

8.1.4 Kinetic Modeling for Imaging Quantification to Calculate Myocardial Uptake, MBF, and Retention

Carimas software incorporates the needed compartmental models suitable for this study. [⁶⁸Ga]Galmydar MBF (at rest and stress) will be quantitatively analyzed using a 1-compartment tracer kinetic model as used previously for other mitochondrial targeted agents.⁵² The standard 1-compartment model is governed by two rate constants: K1 represents activity from blood to myocardium, and is related to blood flow and K2 characterizes the activity from myocardium to the blood. In general, blood flow is related to K1 by a flow-dependent extraction fraction with a relationship of the form: $K1 = EF \text{ (Extraction Fraction)} \cdot MBF$ with $EF = (1 - \exp(-(\alpha MBF + \beta) / MBF))$ with α and β being tracer dependent parameters. Importantly, [¹³N]-NH₃ is a validated quantitative blood flow tracer which will be modeled using the 2-compartment model described earlier. Further, [¹³N]-NH₃ shows first pass extraction of 90% and will serve as a reliable reference control. In both of these models, the effects of partial recovery of the counts in the myocardium and spill-over from the blood pool have been fitted along the model parameters.

To investigate the relationship between the radiotracer extraction and flow, the tracer-derived MBF data will be plotted against both the absolute microsphere-derived MBF values and ¹³N-ammonia MBF values. This relationship will allow us to characterize the flow dependent extraction fraction for the radiotracer. We will first determine K1 from compartmental modeling and then determine the extraction fraction parameters (α and β) by relating [⁶⁸Ga]Galmydar K1 to radioactive microsphere MBF and [¹³N]-NH₃ derived MBF. We will then compare and analyze this extraction fraction to flow dependent extraction of other known MBF tracers, such as ^{99m}Tc-sestamibi, ^{99m}Tc-Tetrafosmin, ²⁰¹Tl or ⁸²Rb. Furthermore, [⁶⁸Ga]Galmydar excretes from blood pool much faster than ^{99m}Tc-sestamibi due to low logP value, and heart/blood (5min/60 min) ratios in mice are also superior to that of ¹⁸F-Flurpiridaz ([⁶⁸Ga]Galmydar: %ID/g; 12.0/0.1 = 120 REF; ¹⁸F-BMS-747158: 9.5/0.5 = 1914; 120/19 = 6.3 folds), these data point to superior flow dependent

extraction fraction of [⁶⁸Ga]Galmydar than ^{99m}Tc-sestamibi. Furthermore, the MFR (myocardial flow reserve), which is defined as the ratio of maximal to basal MBF, will be compared between the myocardial retention (MFR_{retention}) and SUV-derived data (MFR_{SUV}) versus both either [⁶⁸Ga]Galmydar MFR (MFR_{Galmydar}) or ¹³N-Ammonia MFR (MFR_{Ammonia}). Because myocardial perfusion will be homogeneous, only mean values in the left ventricle will be used in the analysis. These proposed experiments will allow us to accurately measure this factor in an animal model closer to an anatomical reference for application in humans thus providing modeling paradigms to enable quantification of the myocardial blood flow in humans. MBF will also be evaluated with clinically approved software such as QPET or 4DM software⁶⁵ available through our departmental image processing servers (MIM/Vista and Hermes).

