1.2.2 Rest/stress Group

A rest/stress myocardial ¹³N-ammonia PET/CT is clinically indicated for the detection of flow-limiting, obstructive coronary artery disease (CAD). Myocardial perfusion PET provides images of a higher quality than SPECT, due to higher spatial and contrast resolution, higher scanner sensitivity, and accurate attenuation correction. In addition, the concurrent quantification of myocardial blood flow (MBF) affords the assessment of hyperemic MBF during pharmacologic vasodilation and at rest and, thus, the computation of the myocardial flow reserve (MFR= MBF stress/MBF rest). The concurrent assessment of hyperemic MBF and/or MFR aids in the identification and characterization of multi-vessel CAD, microvascular dysfunction, and prognostication.

We will compare the results of [⁶⁸Ga]Galmydar PET/CT MPI to the results of ¹³N-ammonia PET/CT MPI in a group of 20 symptomatic patients and 10 normal control subjects without symptomatology. Half of the symptomatic patients recruited will have a SPECT MPI study positive for ischemia in two myocardial segments with referral for invasive coronary angiography (ICA) as part of their routine standard-of-care (n=10), and half with normal SPECT MPI and no ICA referral (n=10). Patients referred for ICA will undergo their [⁶⁸Ga]Galmydar and ¹³N-ammonia PET/CT MPI studies prior to intervention. In addition, as a completely normal control, another 10 subjects without symptomatology or known cardiovascular disease will also undergo both ¹³N-ammonia PET/CT MPI and [⁶⁸Ga]Galmydar PET/CT MPI. In total 30 patients or normal human subjects will be studied.

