2 STUDY OBJECTIVES

2.1 Primary Objective

The primary objective of the proposed study is to evaluate the potential of [⁶⁸Ga]Galmydar PET/CT MPI for the noninvasive detection of coronary artery disease. We will evaluate [⁶⁸Ga]Galmydar PET/CT MPI in comparison to ¹³N-ammonia PET/CT MPI to quantitatively assess myocardial blood flow (MBF) in patients with suspected or known coronary artery disease (CAD) undergoing clinical SPECT MPI. In addition, perfusion and MBF findings with [⁶⁸Ga]Galmydar will be compared to the results of coronary morphology or stenosis severity in those patients undergoing invasive coronary angiography (ICA) based on abnormal SPECT MPI. The performance of rest/stress [⁶⁸Ga]Galmydar PET/CT in comparison to ¹³N-ammonia PET/CT in normal subjects without cardiovascular disease will be performed as a control.

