4.1 Study Population

We will recruit up to 38 participants for the dosimetry and rest/stress groups. Healthy adult normal volunteers (n=8, 4 males; 4 females) for whole-body imaging (dosimetry group) and patients who had a prior clinical SPECT MPI examination that is positive or negative for ischemia.

Thirty (30) subjects will be enrolled in the rest/stress group. Symptomatic patients (n=20) will have undergone a SPECT MPI examination. Ten patients in this group will have had a study positive for ischemia in two myocardial segments and referred for invasive coronary angiography (ICA) as part of their routine standard-of-care. [⁶⁸Ga]Galmydar PET imaging will occur prior to intervention. The other ten patients will have a normal SPECT MPI and no ICA referral. Subjects (n=10) who are asymptomatic and without history of cardiovascular disease will serve as a normal controls.

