9 STATISTICAL PLAN

Continuous variables will be expressed as mean (or median) and range or standard deviations. Categorical variables will be expressed as frequencies. The diagnostic efficacy of [⁶⁸Ga]Galmydar and ¹³N-ammonia PET MPI will be assessed following blinded and independent reads of PET MPI data using ICA as the truth standard. Analysis of diagnostic efficacy will be performed by the reader. The analysis of diagnostic certainty will be a modified majority rule in which the median rating will be used when three readers have 3 different ratings. Similarly, summaries and comparisons of Summed Stress Score (SSS), the Summed Rest Score (SRS), and the Summed Difference Score (SDS) measures will use the median of the results of 3 blinded readers. The sensitivity and specificity and corresponding 95% confidence interval of each radiotracer will be reported. Normalcy rate will be determined in the patients with a low likelihood of CAD and no ICA and be calculated as % of patients with normal/probably normal studies. Agreement for the diagnostic efficacy (presence/absence of CAD) between [⁶⁸Ga]Galmydar and ¹³N-ammonia PET MPI will be compared using a kappa statistic. The agreement between the quality of scan will be assessed using a weighted kappa and the SUV uptake will be assessed using an intra-class correlation coefficient. The ROC analysis will be performed using 17 segment model (according to the American Heart Association Guidelines) to assess the diagnostic efficacy in detection of obstructive coronary disease. The area under ROC and confidence intervals will use the empirical approach developed by DeLong, et al.⁶⁸ The inter-reader agreement between 3 blinded readers will be estimated by comparison of dichotomized ratings (normal/abnormal) and presented using kappa and percent agreement. Intra-reader agreement in each of the reader will be performed by randomizing 10% of the repeat images in the blinded read and will be estimated using kappa and percent agreement. All tests will be two-sided and a significance level of 5%.

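### The primary objective includes a comparison of Galmydar PET with stenosis severity, but every angiographic analysis in the plan uses only CAD present or absent, so severity is never analysed.

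*Combined protocol and SAP*

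**What the plan says.** - **Objective.** Section 2.1, under the primary objective, says that Galmydar perfusion and flow findings "will be compared to the results of coronary morphology or stenosis severity in those patients undergoing invasive coronary angiography (ICA").
- **Measurement.** Section 8.1.3: "All coronary angiograms will be interpreted using quantitative coronary analysis (QCA"). This method yields a graded percent diameter stenosis.
- **Derived variable.** The same section then sets a cut: "A coronary stenosis will be considered present when there is = 50% diameter stenosis in any epicardial coronary artery". The sign before 50% was probably lost when the PDF was read, and nothing here turns on it. From this comes one result per patient: "The presence of one or more coronary stenosis will be used to define the presence of significant CAD". Arteries with stents or grafts have their own rules, for example "arteries with patent stents will be classified as no significant CAD, regardless of evidence of prior myocardial infarction".
- **Analysis.** Section 9 uses angiography as the truth standard for diagnostic efficacy. It plans sensitivity and specificity with 95% confidence intervals, and a ROC analysis on the 17-segment model "to assess the diagnostic efficacy in detection of obstructive coronary disease", with DeLong intervals. It names no analysis of percent stenosis.
- **Patients.** Section 1.2.2 has half of the symptomatic patients entering "with referral for invasive coronary angiography (ICA) as part of their routine standard-of-care (n=10"). Section 4.1 describes them as "positive for ischemia in two myocardial segments and referred for invasive coronary angiography (ICA"). The SPECT-normal patients have no angiography referral, and none is planned for the controls.

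**The concern.** Severity is a graded quantity and the plan already measures it on a graded scale. The only variable that it defines from that measurement separates patients above the cut from those below it. Two patients with 55% and 95% stenosis carry the same value, so the variable cannot show whether the PET findings worsen as stenosis worsens. If Section 9 is followed as written, this part of the primary objective is left without an answer.

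The binary result is also a poor substitute in this sample. All patients with angiography were selected for ischemia on SPECT and for referral, which tends to raise the proportion with significant CAD. If few are CAD-negative, the binary variable hardly varies and specificity rests on a handful of people.

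**Working it through.** **Inputs from the documents.** Ten patients with planned angiography (Sections 1.2.2 and 4.1); the 50% cut (8.1.3); two-sided 5% tests (9); the sample size statement (9.1).

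**Assumptions, not in the documents.** CAD prevalence among the ten: 50% to 90%. Correlation between one PET measure and percent stenosis: 0.5 to 0.8, bivariate normal.

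**1. The plan's own figure.** Section 9.1 reports a kappa interval for 20 patients. 0.8 ± 1.96 × 0.3/√20 = 0.8 ± 0.1315 gives 0.669 to 0.931, width 0.263. It reproduces. It concerns agreement between the two tracers. The documents give no power or precision for any comparison with angiography.

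**2. Few CAD-negatives.** With prevalence p, P(no negative) = p^10 and P(at most one) = p^10 + 10(1−p)p^9.

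| Assumed prevalence | Expected negatives | P(none) | P(at most one) |
|---|---|---|---|
| 90% | 1 | 35% | 74% |
| 80% | 2 | 11% | 38% |
| 70% | 3 | 3% | 15% |
| 50% | 5 | 0.1% | 1% |

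**3. Effect on the planned outputs, per patient.** If all k negatives are read correctly, the exact 95% lower limit for specificity is 0.025^(1/k): 0.025 for k=1, 0.158 for k=2, 0.292 for k=3. The DeLong variance divides by the number of negatives minus one, so the AUC interval is undefined with one negative.

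**4. What the cut costs, as a yardstick.** Simulated sets of ten patients, two-sided 5%, one PET measure. The continuous analysis is a Spearman test (critical value 0.648). After the cut, the PET measure is compared between CAD groups by exact Wilcoxon rank-sum. The plan names neither test; they serve only to put both scales on one footing.

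| Correlation | Continuous | Cut, 90% prevalence | Cut, 80% | Cut, 70% | Cut, 50% |
|---|---|---|---|---|---|
| 0.5 | 27% | 5% | 10% | 13% | 16% |
| 0.6 | 39% | 7% | 14% | 19% | 23% |
| 0.7 | 56% | 9% | 21% | 28% | 33% |
| 0.8 | 76% | 13% | 30% | 41% | 49% |

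The continuous analysis has the higher power in every cell. The test after the cut matters somewhat: at correlation 0.7 and 90% prevalence, a pooled t-test gives 18% where the exact test gives 9%.

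**5. What the continuous scale can deliver.** For an observed Spearman correlation of 0.7 with n=10, an approximate 95% interval is tanh(atanh 0.7 ± 1.96 × √(1.06/7)) = tanh(0.867 ± 0.763), or 0.10 to 0.93. That is informative but wide.

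**The case against.** Several points on the other side stand.

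- **No rank-sum test is planned.** Against angiography, Section 9 plans estimates with intervals. With one negative the smallest exact two-sided rank-sum p-value is 2/10 = 0.20, so a reader might infer that no result could reach the plan's 5% level. That would fault a test that the documents do not contain.
- **Prevalence is unknown.** A reader might infer that nearly all ten patients will be CAD-positive and that power is close to nil. Selection makes a high prevalence plausible, but no figure is given. The patent-stent rule can add negatives, because Section 4.2.2.2 excludes PCI only within six months before SPECT or between SPECT and PET. At 50% to 70% prevalence the power after the cut is low (13% to 49%), not negligible.
- **Percent stenosis is not said to be discarded.** Section 8.1.3 simply derives nothing else from it. It also classifies individual arteries, and the ROC uses a segment model, so it is not established that every analysis has one value per patient.
- **The objective offers an alternative.** It refers to morphology or severity, and a stenosis present/absent result is arguably a finding on morphology.
- **The sample is the larger limit.** This is a phase 0/1 study sized for kappa between tracers. Even the continuous test has only 39% to 56% power at correlations 0.6 to 0.7.
- **A careless remedy brings its own problems.** Correlating three measures for each of two tracers makes six tests. At 0.05/6, Spearman power falls to about 13%, 23% and 42% at correlations 0.6, 0.7 and 0.8.

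These points limit the claim about power and shape the remedy. None of them supplies an analysis of severity.

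**Conclusion.** The point holds as a missing analysis. The primary objective includes stenosis severity, the measurement is already planned, and Section 9 uses only disease presence or absence.

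The gap itself rests on the text alone and needs no assumption. Its size does rest on assumptions. At correlation 0.7, single-test power is 56% on the continuous scale against 9% to 33% after the cut, for prevalence 90% down to 50%. The direction is the same at every prevalence and correlation tried. The chance of at most one CAD-negative patient (74%, 38% or 15% at 90%, 80% or 70% prevalence) depends wholly on the assumed prevalence.

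The documents do not support saying that the angiographic comparison has almost no power, or that a planned test is bound to fail. With ten patients, neither scale gives a firm answer. This is a cheap improvement and does not call the trial's design into question.

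**What to change.** Add to Section 9, in substance:

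- In patients with ICA, one named Galmydar measure (for example SSS or stress MBF) will be related to the maximum QCA percent diameter stenosis per patient, by Spearman correlation with a 95% confidence interval. This is the analysis of the severity objective.
- The other Galmydar measures, and all ¹³N-ammonia measures, will be related to percent stenosis descriptively.
- Sensitivity and specificity at 50% will still be reported.
- State how stented and bypassed arteries enter the maximum, consistent with the rules in Section 8.1.3.

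Naming one measure avoids the problem of six tests. Emphasis should fall on the interval rather than the p-value.

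A per-vessel analysis should be added only after Section 8.1.4, which restricts analysis to mean left ventricular values, is reconciled with Section 8.1.2, which reports regional flow. The paragraph in 8.1.4 also describes microsphere work in an animal model, so its application to patients needs to be stated. Any per-vessel model must allow for several vessels within a patient.

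Cost: a few sentences and one small extra analysis. It needs no further patients, visits or procedures, because QCA is already planned. The downside is a wide interval.

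### Section 8.1.4 assumes homogeneous perfusion and keeps only left-ventricular means, yet ten of 30 subjects are enrolled for regional ischaemia, and Section 9 names no MBF or MFR comparison between tracers

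*Combined protocol and SAP*

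**What the plan says.** Section 2.1 makes blood flow part of the primary objective. Galmydar PET is to be compared with 13N-ammonia PET "to quantitatively assess myocardial blood flow (MBF) in patients with suspected or known coronary artery disease (CAD) undergoing clinical SPECT MPI". Galmydar perfusion and MBF findings "will be compared to the results of coronary morphology or stenosis severity in those patients undergoing invasive coronary angiography".

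Section 4.1 puts 30 subjects in the rest/stress group: ten SPECT-positive patients, ten SPECT-negative patients and ten asymptomatic controls. On the first group it says: "Ten patients in this group will have had a study positive for ischemia in two myocardial segments".

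Three sections deal with the unit of analysis:

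- 8.1.1: "The myocardial wall segment analysis will be performed using the 17-segment American Heart Association model".
- 8.1.2: "Absolute regional myocardial blood flow will also be reported".
- 8.1.4, directly after the MFR comparisons: "Because myocardial perfusion will be homogeneous, only mean values in the left ventricle will be used in the analysis".

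Section 8.1.4 also says that 13N-ammonia "will serve as a reliable reference control". It derives the extraction parameters alpha and beta by relating Galmydar K1 to microsphere flow and to ammonia flow, and adds: "These proposed experiments will allow us to accurately measure this factor in an animal model".

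Section 9 lists kappa for diagnosis, weighted kappa for image quality, an ICC for SUV uptake, summed scores, sensitivity and specificity, normalcy rate and ROC. It mentions neither MBF nor MFR. Section 9.1 sizes the study on kappa alone.

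**The concern.** A regional disease is being summarised by a global mean. In the patients who matter most for the objective, flow is expected to be low in part of the ventricle and normal elsewhere. Averaging over the whole ventricle removes most of that contrast, so a tracer that misreads flow in a small ischaemic territory would look almost the same as ammonia. Angiography is read artery by artery, and a single ventricular mean cannot be assigned to the stenosed vessel.

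Section 9 does not fill the gap. Sections 8.1.1 and 8.1.4 promise a comparative flow evaluation, plots and an MFR comparison, but give no agreement statistic, no unit of analysis and no handling of several segments per subject.

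There is a related problem. Ammonia flow is used to fit alpha and beta and is then the comparator, so agreement on the overall mean is largely built in. Any error specific to diseased myocardium can be seen only if bias is reported by group.

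**Working it through.** **Inputs from the documents.** Ten SPECT-positive patients among 30 subjects, ischaemia in two segments (4.1); 17 segments (8.1.1); two-sided 5% tests (Section 9).

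**Assumptions.** Equal segment weights; a regional stress-flow deficit *d* of 30, 50 or 60% in *k* segments; SD of between-tracer differences of 10, 15 or 20% on the left-ventricular (LV) mean and, deliberately noisier, 30, 40 or 50% regionally. The documents give none of these.

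**The plan's own figure.** 0.8 ± 1.96 × 0.3/√20 = 0.669 to 0.931, width 0.26. This reproduces Section 9.1, but it concerns kappa for diagnosis and says nothing about MBF or MFR precision.

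**Step 1: dilution.** Fall in LV mean = *d* × *k*/17.

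| Segments affected | d = 30% | d = 50% | d = 60% |
|---|---|---|---|
| 2 | 3.5% | 5.9% | 7.1% |
| 6 | 10.6% | 17.6% | 21.2% |

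**Step 2: Galmydar misses the deficit completely.** Excess over ammonia on the LV mean = 1/(1 − *dk*/17) − 1. Excess in the affected segments = 1/(1 − *d*) − 1.

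- *k* = 2, *d* = 50%: 17/16 − 1 = 6.25% on the mean; 1/0.5 − 1 = 100% regionally.
- *k* = 2, *d* = 30%: 3.7% on the mean; 1/0.7 − 1 = 42.9% regionally.
- *k* = 6, *d* = 50%: 17/14 − 1 = 21.4% on the mean; 100% regionally.

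**Step 3: power in ten patients.** Two-sided paired t-test, noncentral t with 9 degrees of freedom and noncentrality difference × √10/SD.

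| Case | LV mean, SD 10/15/20% | Regional, SD 30/40/50% |
|---|---|---|
| 2 segments, 50% | 42/22/14% | above 99% throughout |
| 2 segments, 30% | 18/11/8% | 98/85/68% |
| 6 segments, 50% | >99/98/85% | above 99% throughout |

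The loss is severe for a territory of the size named in the entry criterion and modest for a large one.

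**Step 4: calibration.** Model: K1 = F(1 − exp(−(αF + β)/F)), F being flow. Assumed: α = 0.3, β = 1.5; 10% noise on K1 and on ammonia flow; rest flow 0.9; stress flow 2.6 without CAD and 1.6 or 2.4 with CAD; Galmydar K1 10% or 20% too low in CAD; 300 replicates. Bias = (Galmydar − ammonia)/ammonia.

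| Fit of α and β | K1 error | Overall bias | CAD bias (CAD stress flow 1.6 / 2.4) | SD of CAD bias, points |
|---|---|---|---|---|
| All 30 | 10% | +0.9 to +1.6% | −8.5 / −9.8% | 2.9 to 3.7 |
| All 30 | 20% | +0.9 to +1.6% | −17.6 / −20.1% | 2.9 to 3.7 |
| Ten controls | 10% | not computed | −14.7 / −13.7% | 4.5 to 6.1 |
| Ten controls | 20% | not computed | −27.7 / −27.8% | 4.5 to 6.1 |

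The ranges for overall bias and SD span both error sizes and both CAD flows. With the all-subject fit, the overall mean looks almost unbiased while the CAD group is clearly wrong. A report by group shows it.

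**The case against.** The strongest reply is that the sentence was never meant for these patients. The neighbouring text on microspheres and an animal model suggests it was carried over from a preclinical plan, and its position after the MFR comparison may limit it to MFR. Sections 8.1.1 and 8.1.2 show that segmental work and regional flow were intended. On this reading the correction is editorial. The study is also a small phase 0/1 feasibility study, sized only on diagnostic kappa.

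Much of this is fair as to cause. But the sentence stands as the rule for human data, an analyst cannot follow it and 8.1.2 together, and even an MFR-only reading averages MFR over the ventricle in ischaemic patients. A promise to report regional flow is not an analysis of it. The 17-segment ROC in Section 9 does not say whether its input is visual score or flow, and it would not measure agreement in MBF.

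The power contrast is rightly called illustrative. The SDs are assumed, total failure to see the deficit is an extreme case, and the location of the affected segments is taken as known. If Galmydar missed only a quarter of a 50% deficit, the regional difference would be 0.625/0.5 − 1 = 25%, with power of 65/42/29% at SD 30/40/50%, against 7/6/6% on the LV mean at SD 10/15/20%. The direction holds; the figure above 99% does not. Section 4.1 also does not say whether two segments is a minimum or an exact count.

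The calibration figures depend on an assumed model, and control-only fits can become unstable if alpha is left unbounded. That ammonia is both calibrator and comparator follows from the text without simulation.

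**Conclusion.** The concern holds, and the plan must be changed on this point. The homogeneity premise contradicts the study's own enrolment, the rule to use only LV means contradicts 8.1.1 and 8.1.2, and a named part of the primary objective has no statistic in Section 9. This rests on the text alone.

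The size rests on assumptions. With equal weights, averaging keeps 2/17, about one-eighth, of a two-segment deficit. On LV means in ten patients, a complete miss of a 30 to 50% deficit would usually go undetected at the assumed SDs. The loss is far smaller for six-segment territories.

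The damage is confined to quantitative MBF and MFR. Visual 17-segment scores, summed scores, sensitivity/specificity and ROC on those scores are untouched.

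**What to change.** - In 8.1.4, delete the homogeneity sentence and the animal-model and microsphere text. No microspheres are scheduled, so name 13N-ammonia as the human reference for alpha and beta.
- In Section 9, add a between-tracer comparison of rest MBF, stress MBF and MFR by vessel territory or segment: Bland-Altman bias and limits of agreement, and an ICC, with subject as the cluster.
- Report it separately for SPECT-positive patients, SPECT-negative patients and controls. Keep the LV mean as a secondary summary.
- For patients with angiography, relate territory MBF and MFR to the quantitative stenosis of the supplying vessel.
- State that overall mean agreement is not independent validation, because ammonia is also the calibrator. A calibration in controls only can be an optional sensitivity analysis.

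The first two items follow directly from the text; the exact statistics and grouping are open to the trial statistician's preference.

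The cost is wording and some analysis time, since the dynamic data and segmental software are already planned. Regional MBF is noisier than the LV mean, and groups of ten give wide limits of agreement: the 95% half-width for a mean difference is 0.72 SD at n = 10, against 0.37 SD at n = 30. Control-only calibration is less precise, with about 1.5 to 1.8 times the SD of CAD bias in the simulation.
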